STIMULANT OXYTOCIN STUDY

NCT03016598

[figure not shown]
12/18/2017

Study Protocol

RESEARCH DESIGN

We conducted a randomized, double-blind, placebo-controlled study to examine the effects of oxytocin administration on stimulant use, psychosocial treatment engagement, and stress-reactivity in a sample of 40 individuals with stimulant use disorder receiving opioid agonist therapy within an opioid treatment program at the San Francisco and Oakland VA. Following successful screening and an initial baseline visit, participants were randomized to receive either oxytocin 40 IU or placebo intranasally twice daily for six weeks.

FIGURE 1

Research Participants:

We enrolled 40 male research participants with active stimulant use disorder and stabilized on opioid agonist therapy in an opioid treatment program (OTP). OTP clinics operate under strict state and federal guidelines for treatment structure and monitoring. Each patient receiving opioid agonist therapy from the OTP who is actively using stimulants is in “Phase 0” within the OTPs at the San Francisco and Oakland VA. Phase 0 patients must report to the clinic every day the clinic is open for observed opioid agonist dosing (i.e., no take-home doses), must submit urine for random toxicology screening approximately once every two weeks, and are required to attend weekly psychoeducation/therapy groups within the clinic. All patients in the OTP are assigned an individual counselor who meets with them at least monthly to support the lifestyle changes necessary to progress in recovery. Phase 0 patients typically meet with their counselors more frequently.

Recruitment: Participants were recruited from the OTP through the use of flyers posted visibly in clinic common areas and referrals from clinic counselors who were made familiar with inclusion/exclusion criteria through presentations at staff meetings and “Dear Provider” letters.

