Adherence Monitoring: Study staff trained in proper spray application (Guastella, Hickie, et al. 2013) intranasally administered participants’ morning study drug doses. Each participant was given a nasal spray bottle and trained in proper spray application by study staff. Participants were to administer their evening dose 8-10 hours following their morning dose. Each week, participants will be incentivized to bring their nasal spray bottle from the previous week, whether full or empty, for adherence monitoring via weighing. We successfully used similar contingent management strategies in our previous study of

repeated oxytocin administration in patients with co-occurring cocaine and opioid use disorders. Our participants brought their nasal spray devices in for weighing 98% of the time (no participant forgot more than once) and collectively self-administered >78% of their evening doses.

Randomization: Participants were randomized 1:1 to receive either oxytocin or placebo. A randomization plan was created using www.randomization.com. Randomization was managed by the Investigational Drug Pharmacist at the San Francisco VA, who also managed the double blind.

Inclusion Criteria: Participants must be at least 18 years old, enrolled as a patient at the San Francisco or Oakland VA OTP, be on a stable dose of methadone or buprenorphine for at least two consecutive weeks, and have at least one documented routine urine toxicology screen positive for cocaine or methamphetamine in the past month.

Exclusion Criteria: Urine toxicology screen positive for heroin in the past month; meeting *Diagnostic and Statistical Manual of Mental Disorders, 5th Edition* (DSM-V) criteria for previous or current psychotic disorder, severe neuropsychological disorder, premenstrual dysphoric disorder, or current moderate severe alcohol use disorder; active suicidal or homicidal ideation; hemodialysis; sensitivity to E 216, E 218, and chlorbutanol hemihydrate (preservatives used in nasal spray); using hormone supplementation; positive urine pregnancy test or women of child-bearing age not practicing an effective means of non-hormonal birth control; or nasal obstruction, discharge, or bleeding.

METHODS

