#### Data Analysis:

Aim 1: We will employ linear mixed effects models to examine within- and between-group variability in positive stimulant urine drug screens across 6 weeks.

Aim 2: We will employ linear mixed effects models to examine within- and between-group differences in (H2) client and therapist WAI ratings and (H5) attendance rates.

Aim 3: We will use linear mixed effects models to assess within- and between-group differences in the following stress measures related to the Trier Social Stress Test (conducted at baseline and post-6 weeks): (H3) Psychophysiological measures (HR, HRV), (H4) self-reported stimulant craving, (H6) salivary stress biomarkers (cortisol and DHEA), and (H7) self-reported anxiety (STAI-6).

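### Clinic (San Francisco or Oakland) appears in neither the described randomisation nor the supplied models; a site term would be a cheap, minor gain where arms are compared as levels, chiefly on attendance

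*SAP*

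**What the plan says.** The Protocol (Research Participants) places the trial "within the OTPs at the San Francisco and Oakland VA", and the Inclusion Criteria accept anyone "enrolled as a patient at the San Francisco or Oakland VA OTP". So there are two clinics, and no quota or split between them is given. On size, the same part of the Protocol states: "We enrolled 40 male research participants with active stimulant use disorder".

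The Randomization paragraph reads: "Participants were randomized 1:1 to receive either oxytocin or placebo. A randomization plan was created using www.randomization.com". The plan was held by the investigational pharmacist at San Francisco. Stratification, blocking and a separate list for each clinic are not mentioned.

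The Data Analysis section of the SAP names linear mixed effects models for all three aims and describes them only by within- and between-group comparison. For Aim 2 it says: "We will employ linear mixed effects models to examine within- and between-group differences in (H2) client and therapist WAI ratings and (H5) attendance rates". No site term, counselor term or other covariate is named, and the section does not say which model term carries the test of oxytocin against placebo. One part of the SAP was not available, so this describes the supplied text only.

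**The concern.** Clinic is known at entry and cannot be changed by treatment, so it is a natural covariate. Two Aim 2 outcomes are tied to it by the Protocol's own description: attendance is attendance at the participant's own clinic, and the WAI-SR is completed by and about a counselor whom that clinic assigned. If clinics differ on such an outcome, and by chance one arm holds more participants from one clinic, part of the clinic difference appears as an arm difference. Even without imbalance, the clinic difference stays in the residual variance. With about 20 per arm, sizeable imbalances are not rare.

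How much this matters depends on the contrast. It applies to outcomes compared between arms as levels. Attendance is the clearest case because no baseline for it is stated. Urine positivity and WAI-SR join it only if the tested term is a post-baseline group difference.

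**Working it through.** The supplied text gives no power, alpha, SD or effect size, so there is no figure of the plan's own to reproduce.

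**Inputs from the documents.** Total 40 (Research Participants); 1:1 allocation (Randomization); two clinics (Research Participants, Inclusion Criteria).

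**Assumptions.** Arms of exactly 20 and 20; no stratification by clinic; K of the 40 at the smaller clinic; two-sided alpha 0.05; the size of any clinic difference.

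**1. Size of chance imbalance.** Let x be the number of smaller-clinic participants in the oxytocin arm. Then x is hypergeometric (40 in total, K at the smaller clinic, 20 drawn). The difference in clinic share between arms is (2x − K)/20. Its SD is √[20 × (K/40) × (1 − K/40) × (20/39)] / 10.

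| K | SD of difference | P(difference of 20 points or more) |
|---|---|---|
| 3 | 0.084 | 0 (maximum is 3/20 = 15 points) |
| 4 | 0.096 | 0.11 |
| 6 | 0.114 | 0.18 |
| 10 | 0.139 | 0.27 |
| 14 | 0.153 | 0.32 |
| 20 | 0.160 | 0.34 |

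For example, with K = 4 a 20-point difference needs all four in one arm: 2 × C(20,4)/C(40,4) = 2 × 4,845/91,390 = 0.106. A difference of 30 points or more has probability 0.04 with K = 8 and 0.11 with K = 20.

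**2. Shift in a level contrast.** Shift = imbalance × clinic difference. A 20-point imbalance with an assumed clinic gap of 10, 20 or 30 points gives 0.20 × 10 = 2, 0.20 × 20 = 4 or 0.20 × 30 = 6 points.

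**3. Type I error.** Take a continuous outcome with within-clinic SD 1, a clinic gap of g SD, an even clinic split and 20 per arm. The unadjusted test rejects beyond c = 1.96 × √(1 + g²/4) × √(2/20). Given the imbalance, the estimate is centred at b = imbalance × g with SD s = √(2/20) = 0.316. The conditional error is 1 − Φ((c − b)/s) + Φ((−c − b)/s).

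- At 20 points: 0.051, 0.054 and 0.059 for g = 0.2, 0.5 and 0.8.
- At 30 points: 0.053, 0.067 and 0.090.
- Averaged over all randomisations (40,000 simulated trials): 0.049 for g = 0.5 and 0.050 for g = 0.8. Overall error is not inflated.

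**4. Precision.** For an effect that the unadjusted comparison detects with 80% power, a site term gives power of about Φ(2.80 × √(1 + g²/4) − 1.96): 80.4%, 82.3% and 85.5% for g = 0.2, 0.5 and 0.8. This ignores the lost degree of freedom and residual imbalance.

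**5. Change from baseline.** With complete data, the group-by-time estimate is the difference between arms in mean within-person change. A constant clinic effect is the same at every visit for a given person and subtracts out. Simulated random-intercept models with and without a site main effect (0.8 SD clinic gap, unbalanced arms) gave identical group-by-time estimates: −0.1955 both ways with two time points, −0.0114 both ways with seven. Only a clinic difference in change would pass through, and a site main effect does not remove that.

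**The case against.** A reader might infer that a clinic imbalance feeds straight into every oxytocin-placebo comparison in Aims 1 to 3. The documents do not support that. Urine screens are collected at baseline and weekly, and the WAI-SR and the stress-test measures are taken at baseline and again at six weeks. If the tested term is group-by-time, stable clinic differences largely cancel and a site main effect changes little. This part of the objection stands and limits the point to level contrasts.

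Three further objections carry weight:

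- **No clinic difference is documented.** The Protocol describes one common structure at both clinics: daily observed dosing, urine screening about every two weeks, weekly groups and individual counselors. Differences in patient mix or drug supply are nowhere stated. For attendance, participants must report on every open day and the SAP analyses a rate; if its denominator is open days, a difference in opening schedules drops out. The gaps used above are therefore illustrations.
- **The split is unknown.** The chance of about a third belongs to near-even clinics. It falls to 11% with 4 participants at the smaller clinic and to zero with 3 or fewer.
- **The unadjusted test is valid.** Randomisation holds its overall error near 0.05.

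Finally, the point rests on silence in a short text, part of which was not available. The Randomization paragraph does not describe stratification, which does not show that there was none.

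What survives is narrow: clinic is a known baseline factor linked by design to attendance and counselor ratings, and using it costs almost nothing.

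**Conclusion.** The point holds as a minor improvement. On the supplied text, clinic is used in neither randomisation nor analysis. For attendance, and for urine positivity or WAI-SR if they are compared as post-baseline levels, this leaves avoidable chance bias in the realised estimate and some avoidable residual variance.

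Its size rests on assumptions about the clinic split and the clinic gap, neither of which the documents give. If the clinics barely differ, or nearly all participants came from one, the effect is negligible. It would be wrong to conclude that the tests are invalid, that type I error is inflated overall, or that Aim 3 is compromised: no Aim 3 outcome is shown to depend on clinic, and those measures have baselines. If the unavailable part of the SAP already includes site, the point falls.

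**What to change.** Before unblinding:

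- State which term in each model carries the test of oxytocin against placebo.
- Add site (San Francisco or Oakland) as a fixed effect to the Aim 2 attendance model, and to any Aim 1 or WAI-SR model whose tested term is a between-arm level. Two clinics are too few for a random effect. The oxytocin-placebo contrast remains the estimate. A site term is optional for Aim 3.
- Say whether randomisation was stratified by clinic. If it was, the site term is still appropriate because the analysis should reflect the design.
- Report the number of participants by arm and clinic.

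The cost is a few sentences in the SAP and one degree of freedom in each model concerned. No new data are needed, since eligibility already records each participant's clinic.

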- 2) a. **Working Alliance Inventory – Short Revised (WAI-SR):** (Hatcher & Gillaspy, 2006): is a well-validated 12-item measure of therapeutic alliance. Participants completed individual “client forms” for their clinic-assigned individual counselor at baseline and after six weeks. Likewise, the counselor completed the “therapist form” for each participant at baseline and after six weeks of study participation. Time required for administration per form: <5 minutes.
b. **Attendance in OTP clinic:** Daily attendance at OTP clinic was tracked for each participant.

FIGURE 2

Psychophysiology measurements
Baseline CCQ-Brief, salivary biomarkers, Likert scales
Figure 6: Social Stress-Induced Cocaine Craving Paradigm. TSST = Trier Social Stress Test, CCQ-Brief –Cocaine Craving Questionnaire-Brief, salivary biomarkers = cortisol and dehydroepiandrosterone, Likert scales = subjective stress and anxiety.

- 3) **Trier Social Stress Test (TSST) (see Figure 2):** in order to evaluate response to social stress, participants engaged in the TSST paradigm at study baseline and after six weeks of intranasal oxytocin or placebo. The TSST is a standardized and well-validated psychological stress challenge which has shown utility for evoking a strong cardiovascular and HPA axis stress response (including salivary cortisol) in a laboratory setting (Dickerson & Kemeny 2004). After a 5-minute preparation period, participants are instructed to give a speech and perform serial subtractions, for five minutes each, in front of a panel of stone-faced adjudicators.
 - a. **Cocaine Craving Questionnaire-Brief (CCQ-Brief):** (Sussner, Smelson et al. 2006) is a valid and reliable 10-item self-report instrument, with each item scored on a scale 1-7, used to measure the respondent's general cocaine craving. We amended this to also include methamphetamine and asked for participants' stimulant of choice. Participants

completed the amended CCQ-Brief at baseline, immediately after the TSST, and 20 minutes after the TSST.

- b. **Psychophysiological Stress Measures:** consisted of two main outcome variables: *heart rate* and *heart rate variability*. We recorded continuous physiology during the TSST, we will include the 5-min averages for: baseline, speech prep, speech, mental arithmetic, and 15-20 mins post-TSST.

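### Aim 2 does not say how the baseline WAI-SR rating enters the H2 model or which contrast is the arm effect; if the arm baseline means are left free, the comparison is less precise than the collected data allow.

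*SAP*

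**What the plan says.** The Protocol (Outcome Measures, item 2a) gives two ratings per form. For the client form: "Participants completed individual “client forms” for their clinic-assigned individual counselor at baseline and after six weeks". For the therapist form: "the counselor completed the “therapist form” for each participant at baseline and after six weeks of study participation". Under Research Design, baseline precedes randomization and six weeks of treatment, so the baseline rating is a pre-drug measurement.

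The trial is small: "in a sample of 40 individuals with stimulant use disorder receiving opioid agonist therapy". Allocation is equal: "Participants were randomized 1:1 to receive either oxytocin or placebo". That is about 20 per arm.

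The available SAP text on the analysis of H2 (Data Analysis, Aim 2) is: "We will employ linear mixed effects models to examine within- and between-group differences in (H2) client and therapist WAI ratings". It lists no fixed effects, no treatment of baseline and no contrast. Part of the SAP ahead of Data Analysis was not available for this review and may say more.

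**The concern.** With one pre-drug and one post-drug rating, several different analyses fit the Aim 2 sentence, and they are not equally precise. Asking about differences both within and between groups suggests that both ratings enter as outcomes. The usual model of that kind has arm, time and arm-by-time terms. With two visits, its interaction is simply the difference between arms in mean change.

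That contrast is valid under randomization, but it subtracts the whole baseline difference, whereas the data support subtracting only the fraction rho of it when the two visits have equal SDs. The result is extra noise and over-correction of any chance baseline imbalance. At about 20 per arm the WAI-SR comparison has little precision to spare, and the baseline rating that would recover some of it is already collected.

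**Working it through.** **Inputs from the documents.** 40 participants, randomized 1:1, so n = 20 per arm (Protocol, Research Design and Randomization). Two ratings per form, at baseline and week 6 (Protocol, Outcome Measures 2a). A linear mixed model with baseline handling unstated (SAP, Data Analysis, Aim 2).

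**Assumptions not in the documents.** No dropout, equal SDs at both visits and in both arms, a two-sided 5% test, a true week-6 effect of 0.8 or 0.5 SD, and a correlation rho between baseline and week-6 WAI-SR of 0.3 to 0.8. The available text states no power, effect size or SD, so there is no planned figure to reproduce.

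**Step 1: variances.** In units of sigma² × 2/n:

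- difference in change (arm baseline means free): 2(1 − rho)
- week 6 adjusted for baseline: 1 − rho²
- ratio: 2(1 − rho) / [(1 − rho)(1 + rho)] = 2/(1 + rho)

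At rho 0.5 the two variances are 1.00 and 0.75, a ratio of 1.33. With 2/n = 0.1 the contrast variances are 0.100 and 0.075 sigma².

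**Step 2: check that the mixed model behaves this way.** In 400 simulated trials (20 per arm, rho 0.5), the arm-by-time estimate equalled the difference in change to rounding (largest gap below 1e-14). Empirical variances were 0.093 for that estimate, 0.068 for the baseline-covariate analysis and 0.068 for a mixed model with a common baseline mean. The last two estimates correlated 0.995. So the loss comes from leaving the baseline means free, not from using a mixed model.

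**Step 3: power.** Noncentral t:

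- Change: noncentrality = d / √[2(1 − rho) × 0.1], 38 df.
- Adjusted: noncentrality = d / √[(1 − rho²)(1 + 1/37) × 0.1], 37 df. The factor 1 + 1/37 is an allowance for estimating the baseline slope.

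Example at rho 0.5, d = 0.8: 0.8/√0.100 = 2.53 gives 69%; 0.8/√(0.75 × 38/37 × 0.1) = 0.8/√0.0770 = 2.88 gives 80%.

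| rho | Variance ratio 2/(1+rho) | Power, 0.8 SD: change vs adjusted | Power, 0.5 SD: change vs adjusted |
|---|---|---|---|
| 0.3 | 1.54 | 55% vs 72% | 26% vs 36% |
| 0.5 | 1.33 | 69% vs 80% | 34% vs 42% |
| 0.7 | 1.18 | 89% vs 93% | 51% vs 57% |
| 0.8 | 1.11 | 97% vs 98% | 68% vs 72% |

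A separate simulation with 10,000 replicates at 0.8 SD gave 69.3% vs 80.4% at rho 0.5 and 88.7% vs 92.6% at rho 0.7, in agreement.

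**Step 4: where the advantage ends.** With the slope cost included, adjustment wins while 2/(1 + rho) > 38/37, that is, rho < 2 × 37/38 − 1 ≈ 0.95.

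**The case against.** The strongest reply is that the SAP commits to no inefficient analysis. Its sentence names a class of model and stops there. A mixed model with a common baseline mean fits that sentence, gives baseline no covariate role, and is as precise as covariate adjustment (Step 2). This stands. A reader might infer that, because no baseline covariate is named, the arm comparison does lose precision. The text does not support that: the loss follows only if the arm baseline means are left free. The unavailable part of the SAP could also settle the matter, and its absence from the review is not a gap in the plan.

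A reader might also take the between-group difference to be a main effect averaged over both visits. That would mix in a pre-drug rating, halve the effect and leave about 30% power at rho 0.5 for a 0.8 SD effect. Nothing in Aim 2 says this. With one rating before and one after treatment, comparing changes is the more natural reading, so this figure should not be used to size the problem.

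Three further points stand. The difference in change is unbiased, so the choice is one of efficiency between valid estimators; the absence of stratification on WAI-SR is no defect. The gain depends on an assumed rho and effect, and is about 1 point at rho 0.8 for a 0.8 SD effect. The Protocol's Methods section makes the urine drug screen the primary outcome, not the WAI-SR.

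What the reply does not remove is the open choice. The common-baseline model is a deliberate constraint that must be stated, and the available Aim 2 text does not state it. Aim 3 uses similar wording for stress measures also taken at baseline and week 6, so the gap is not peculiar to the WAI-SR, but that is no reason to leave it.

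**Conclusion.** The point holds conditionally. The available Aim 2 text leaves the role of the baseline WAI-SR and the H2 contrast undefined. If the usual arm-by-time model is fitted, variance is 11% to 54% higher than necessary for rho from 0.8 down to 0.3 (before the small slope cost). At rho 0.5 that costs about 11 percentage points of power for a 0.8 SD effect and about 8 for 0.5 SD; at rho 0.7 it costs about 4 and 6. These sizes rest on 20 per arm, no dropout, equal SDs and a two-sided 5% test, with rho and the effect assumed.

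There is no material loss if a common baseline mean is already intended, and no point to make if the unavailable SAP text specifies baseline adjustment. No bias is alleged and the primary outcome is untouched. This is a lower-priority efficiency gain, worth taking because the data for it are already in the schedule.

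**What to change.** State in Aim 2 that, separately for the client and therapist forms, the H2 arm effect is the oxytocin-minus-placebo difference in the week-6 WAI-SR score adjusted for the same form's baseline score. Name one of two methods: baseline as a covariate, or a mixed model with both ratings as outcomes and a common baseline mean across arms. The second keeps participants with one missing rating. Report within-arm changes as descriptive.

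The cost is a short addition to the SAP and, with the covariate, one degree of freedom out of 38. No new data, visits or staff are needed. Parts of the Protocol are in the past tense, so WAI-SR data may already be collected. If so, the change should be dated and disclosed as such, with a statement of whether it was made before unblinding.

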All measures are listed in detail below. In sum, our primary outcome measure will be **(1)** Stimulant positive urine drug screen collected at baseline and weekly throughout the study. To assess psychosocial measures, participants and their clinic assigned counselor will complete **(2a)** the Working Alliance Inventory – Short Revised (WAI-SR) (Hatcher & Gillaspy 2006), client and therapist forms, respectively, at baseline and after six weeks as well as **(2b)** OTP attendance rates. Additionally, in response to a Trier Social Stress Test, we will measure, **(3a)** self-reported stimulant craving by completing the Cocaine Craving Questionnaire (CCQ-Brief) modified to include methamphetamine in addition to cocaine, **(3b)** psychophysiological measures, including heart rate and heart rate variability, **(3c)** stress biomarker measurements, including salivary cortisol and DHEA, and **(3d)** self-reported anxiety.

See **Figure 1** for Study Design Outline.

PROCEDURES

Screening/Baseline: Potential participants were screened by study staff on site and, if preliminarily eligible, signed a brief clinic-specific consent in order for us to confirm eligibility via OTP medical records. Eligible participants were invited for a baseline interview, which included: 1) written informed consent, 2) a medical history and brief physical exam conducted by a study physician, 3) a structured mental health interview conducted by an advanced psychology trainee, 4) baseline measurements, and 5) a urine pregnancy test (for female participants).

Daily: We asked participants to report daily on their illicit drug use from the previous 24-hours, including specific drug, amount, and route of administration. We also monitored daily OTP clinic attendance.

Weekly: Participants provide a weekly urine sample, which was analyzed for various drugs of abuse.

MEASURES

[figure not shown]
Screening Measures:

- 1) **Structured Clinical Interview for DSM-5 Disorders – Clinical Trials Version (SCID-5-CT):** a structured psychiatric interview based on current diagnostic standards, customized to the inclusion and exclusion criteria of our clinical trial.

Outcome Measures:

- 1) **Stimulant positive urine drug screen:** (Jufer, Wstadik et al. 2000, Preston, Epstein et al. 2002) was measured from baseline and weekly urine samples. Urine samples were screened for a variety of drugs of abuse.

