- c. **Salivary cortisol and dehydroepiandrosterone (DHEA):** are biological markers of HPA-axis stress reactivity. We will collect salivary cortisol and DHEA at baseline, immediately after the TSST, and 20 minutes after the TSST.
- d. **State-Trait Anxiety Inventory, 6-item version (STAI-6):** participants will rate their levels subjective anxiety using the STAI-6 at baseline, immediately after the TSST, and 20 minutes after the TSST.

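### Aim 3: adjusting the week-6 TSST response for the baseline-visit response is a nearly free gain in precision that the available SAP text does not take up

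*SAP*

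**What the plan says.** The Protocol (Research Design) sets out to "examine the effects of oxytocin administration on stimulant use, psychosocial treatment engagement, and stress-reactivity". Its Methods section introduces the stress outcomes with "in response to a Trier Social Stress Test, we will measure", and the TSST entry under Outcome Measures gives the purpose as to "evaluate response to social stress, participants engaged in the TSST paradigm at study baseline and after six weeks of intranasal oxytocin or placebo". There are therefore two TSST sessions per participant, and the Research Design section places randomisation after the baseline visit.

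Within each session, craving has three values: participants "completed the amended CCQ-Brief at baseline, immediately after the TSST, and 20 minutes after the TSST". Cortisol and DHEA ("We will collect salivary cortisol and DHEA at baseline, immediately after the TSST, and 20 minutes after the TSST") and STAI-6 follow the same three time points. For heart rate and heart rate variability, "we will include the 5-min averages for: baseline, speech prep, speech, mental arithmetic, and 15-20 mins post-TSST", which makes five epochs.

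The SAP (Data Analysis, Aim 3) names linear mixed effects models. Their stated target is "within- and between-group differences in the following stress measures related to the Trier Social Stress Test (conducted at baseline and post-6 weeks"). The available text does not say how the baseline-visit session enters the model.

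**The concern.** The trial has about 20 participants per arm and collects a pre-randomisation TSST response on each of the six Aim 3 measures. That response is a legitimate covariate for the week-6 response. In a mixed model with group, visit and their interaction, and separate group means at the baseline visit, the interaction estimates the unadjusted change in response. With complete data, the week-6 group difference from the same model is the week-6-only comparison. Neither makes best use of the baseline session.

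What is at stake is precision on one of the trial's three stated objectives. The group-by-visit estimate is on target but less precise than the same 40 participants allow. A second, smaller issue is scale. If a measure behaves proportionally, a raw post-minus-pre difference can turn a shift in level into apparent reactivity, whichever visit contrast is used.

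**Working it through.** **Inputs from the documents.** N = 40, allocated 1:1, so n = 20 per arm; two TSST visits; three samples (craving, cortisol, DHEA, STAI-6) or five epochs (HR, HRV) per visit. The available text gives no effect size, SD, correlation, alpha or dropout for Aim 3, so there is no planned figure to reproduce.

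**Assumptions.** Response = post-stressor minus pre-stressor. Its variance V is the same at both visits, and its across-visit correlation is c, shown from 0 to 0.6.

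**Step 1: variance per participant.** Subtracting b times the baseline-visit response from the week-6 response leaves variance V(1 + b² − 2bc).
- Week-6 only (b = 0): V
- Change in response (b = 1): 2V(1 − c)
- Adjusted (b estimated, optimum b = c): V(1 − c²), times 1 + 1/(N − 4) = 37/36 for estimating the slope

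**Step 2: ratios.** Adjusted over change = (1 + c)/2 × 37/36. Adjusted over week-6 only = (1 − c²) × 37/36.

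| c | adjusted / change | adjusted / week-6 only |
|---|---|---|
| 0 | 0.51 | 1.03 |
| 0.3 | 0.67 | 0.94 |
| 0.45 | 0.75 | 0.82 |
| 0.6 | 0.82 | 0.66 |

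Against change, break-even is c = 2 × 36/37 − 1 = 0.95. Against week-6 only, it is c = √(1/37) = 0.16. With 30 completers the factor is 27/26, and the first ratio is 0.68 to 0.83 for c = 0.3 to 0.6.

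**Step 3: in participants.** At c = 0.3 to 0.6, adjusting 40 participants matches a change analysis of 40/0.668 = 60 down to 40/0.822 = 49.

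**Step 4: illustrative power.** Further assumptions: two-sided 5%, no dropout, total SD 1, sample-level variance 0.3, response = mean of both post samples minus pre (V = 1.5 × 0.3 = 0.45), and a true effect of 0.5 SD at both post samples.

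| c | change | week-6 only | adjusted |
|---|---|---|---|
| 0.3 | 49% | 63% | 66% |
| 0.45 | 59% | 63% | 72% |
| 0.6 | 73% | 63% | 81% |

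At c = 0.45, the adjusted 72% falls to 58% with 15 per arm. It falls to about 25% if the effect appears only immediately after the stressor, because averaging both post samples halves it.

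**Step 5: scale.** Let the stressor multiply a level L by k, and let treatment multiply the level by m with no change in k. The raw response goes from L(k − 1) to mL(k − 1), while the log response stays at log k. I simulated the adjusted raw contrast with 20 per arm, log-scale SD 0.6, m = 0.7 and c = 0.45 (all assumed). It rejected in 16% of trials for k = 1.5 and 32% for k = 2, against 5% on the log scale. The raw-scale rate varies with the assumed variances.

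**Step 6: missing baseline response.** If 4 of 40 lack it, a plain covariate model uses 36. The common-baseline-mean model has precision 1 + 4(1 − c²)/36 times as large: 1.10 at c = 0.3 and 1.07 at c = 0.6.

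**The case against.** Part of the SAP was not available. Data Analysis labels its outcomes H2 to H7, and those hypotheses are not stated in the text at hand; they may define the response or the contrast. Linear mixed models also already permit a baseline covariate or a common baseline mean. Both points stand: nothing in the SAP rules adjustment out, so this is an improvement to write in, not an error to correct.

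A reader might infer something stronger: that Aim 3 could be analysed by pooling the within-session samples at each visit, so that a resting-level shift would be reported as changed reactivity. The documents do not support that. The Protocol's wording ("in response to a Trier Social Stress Test, we will measure") and its stated purpose for the TSST point to a within-session response, and no passage describes a pooled analysis. Error rates for a pooled analysis would describe a plan that nobody has stated.

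The gain also depends on the comparator. Against week-6 only at c = 0.3 it is 3 power points (63% to 66%), not the 17 points seen against change (49% to 66%). At c = 0, adjustment costs about 3% in variance. The power figures flatter any contrast that averages the post samples, because they assume an equal effect at both and no dropout. These limits stand. Apart from the small slope-estimation cost, the ranking of adjusted over change does not depend on them, since the change contrast fixes b at 1 where adjustment estimates the best b.

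**Conclusion.** The point holds as a recommendation on efficiency and wording. On the available text, the baseline-visit TSST response has no covariate role, and a standard group-by-visit model would give up precision. Relative to the change contrast, confidence intervals would be about 9% to 18% shorter with adjustment (√0.822 = 0.907; √0.668 = 0.817). Relative to week-6 only, the benefit runs from a slight loss at c = 0 to a variance ratio of 0.66 at c = 0.6.

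The sizes rest on an assumed c and on equal response variance at both visits. Unequal variances would change the sizes, but in large samples adjustment would still be at least as precise as either alternative. The power figures are illustrative only. The unavailable SAP text could already settle the response definition or the adjustment.

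**What to change.** For each Aim 3 measure, state in the SAP that the treatment effect is the between-group difference in week-6 TSST response (post-stressor minus pre-stressor), adjusted for the same response at the baseline visit. Alternatively, model the two visit responses with a mean common to both groups at the baseline visit. This stays within the planned model class and keeps participants without a baseline response.

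Before unblinding, also fix:
- the response summary, meaning which post samples (craving, cortisol, DHEA, STAI-6) or which epochs (HR, HRV) count, a choice that belongs to the sponsor;
- the analysis scale, using logs for cortisol, DHEA and HRV if they behave proportionally;
- separate terms for the baseline visit and the pre-stressor sample, both of which the Protocol calls baseline.

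Do not adjust for the week-6 pre-stressor value, which is measured after randomisation. Report it separately as a resting-level outcome.

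The cost is SAP wording and one degree of freedom (37/36 at N = 40). No new data are needed, since every value is already scheduled.
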